10.3. Analysis of Secondary Endpoints

The MMRM models will be applied to analyze the longitudinal data secondary endpoints. Regression modeling approaches using either the logistic regression model or Cox proportional hazards regression model will be employed for binary and time-to-event endpoints, respectively. All statistical analysis will be conducted using SAS version 9 or higher software. Statistical significance will be defined at the two-sided 0.05 level.

11. Study Administration

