12.2. CONFIDENTIALITY AND HEALTH INSURANCE PORTABILITY AND ACCOUNTABILITY ACT (HIPAA)	
CONSIDERATIONS	31
13. INVESTIGATOR AGREEMENT	33
14. REFERENCES	34

List of Tables

Table 1. Table of Study Visits.

Table 2. Final Diagnosis in the Evaluation of Suspected Acute Exacerbations.

Table 3. Enrollment requirements for varying effect size and power.

List of Figures

Figure 1. Laparoscopic surgery was associated with increased survival compared to no therapy.

Figure 2. Change in FVC before (pre) and after (post) laparoscopic anti-reflux surgery.

List of Abbreviations

6MWD	6-minute walk distance
6MWT	6-minute walk test
ABG	arterial blood gas
AE	adverse event
AEx	acute exacerbation
BAL	bronchoalveolar lavage
CRF	case report form
DCC	Data Coordinating Center
DLCO	diffusing capacity of the lung for carbon monoxide
DSMB	Data and Safety Monitoring Board
eCRF	Electronic case report form
FVC	forced vital capacity
GER	Gastroesophageal reflux
HIPAA	Health Insurance Portability and Accountability Act
HRCT	high-resolution computed tomography
ICECAP-O	ICEpop CAPability measure for Older People
ILD	interstitial lung disease
IPF	idiopathic pulmonary fibrosis
IRB	institutional review board
MOP	Manual of Operating Procedures
NHLBI	National Heart Lung and Blood Institute
NIH	National Institutes of Health (U.S.)
PFT	pulmonary function test
PI	principal investigator
QOL	quality of life
SAE	serious adverse event
SAP	statistical analysis plan
SGRQ	St. George's Respiratory Questionnaire
UCSD SOBQ	University of California at San Diego Shortness of Breath Questionnaire
VAS	Visual Analog Scale

WEIGHING RISKS AND BENEFITS OF LAPAROSCOPIC ANTI-REFLUX SURGERY IN PATIENTS WITH IDIOPATHIC PULMONARY FIBROSIS (WRAP-IPF): A PHASE II CLINICAL TRIAL

1. Summary

This protocol proposes to test the following hypothesis: Treatment with laparoscopic antireflux surgery in subjects with idiopathic pulmonary fibrosis (IPF) and abnormal gastroesophageal (GER) reflux will slow the decline of forced vital capacity (FVC) over 48 weeks.

This study will randomize approximately 58 subjects with IPF and abnormal acid reflux on 24-hour pH monitoring to laparoscopic anti-reflux surgery or standard care (randomization ratio 1:1). Subjects will be followed for 52 weeks or until the time of lung transplantation or death.

2. Hypothesis and Specific Aims

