2.1. Study Hypothesis

Our primary hypothesis is that the reduction of abnormal GER with laparoscopic anti-reflux surgery will slow the progression of IPF as measured by FVC. We further hypothesize that laparoscopic anti-reflux surgery will reduce the frequency of acid reflux, will be safe and well tolerated, will improve symptoms and quality of life, and will reduce the incidence of acute exacerbation, hospitalization, disease progression and death. Specifically, we will address the following aims:

2.2. Specific Aim 1

We aim to determine the impact of laparoscopic anti-reflux surgery on change in FVC over 48 weeks in patients with IPF and abnormal GER.

2.3. Specific Aim 2

We aim to correlate the reduction in acid reflux events with the change in FVC over 48 weeks in patients with IPF and abnormal GER.

2.4. Specific Aim 3

We aim to determine the safety of laparoscopic anti-reflux surgery in patients with IPF and abnormal GER.

2.5. Specific Aim 4

We aim to explore the impact of laparoscopic anti-reflux surgery on key secondary endpoints over 48 weeks in patients with IPF and abnormal GER.

2.6. Specific Aim 5

To identify molecular markers of IPF disease activity and gastroesophageal reflux in biological samples from patients with IPF and abnormal GER.

3. Background and Significance

Idiopathic pulmonary fibrosis (IPF) is a chronic progressive lung disease of unknown cause and increasing prevalence in the United States.^{1,2} An estimated 100,000 Americans will die from IPF this year, and aside from lung transplantation, which only 1% will receive, there is no FDA-approved therapy.

Over the last decade, a potential role for gastroesophageal reflux (GER) in the progression of IPF has been suggested.³ This is based on several observations: First, it is clear that the overwhelming majority of patients with IPF have abnormal GER.⁴⁻⁶ Second, small case series of patients with IPF treated for GER demonstrated stabilization of pulmonary physiology and oxygenation.^{7,8} Third, the treatment of GER has been associated with improved survival in two large, independent retrospective cohorts of patients with IPF.⁹

Importantly, there are no prospective, randomized data addressing the treatment of GER in IPF and there is a real chance that the data collected to date are misleading. A prospective, controlled trial is essential to answer this question.

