6.2. Secondary Endpoints

The secondary endpoints of this study will be:

- Disease progression
- Categorical change in FVC
- Acute exacerbation
- Non-elective hospitalization
- Mortality
- Time to disease progression
- Time to categorical change in FVC, acute exacerbation, or death (composite endpoint)

- Time to non-elective hospitalization or death (composite endpoint)
- Change in UCSD SOBQ score (continuous and categorical)
- Change in SGRQ score (continuous and categorical)
- Change on cough visual analog scale (VAS)
- Change in ICECAP-O score (continuous and categorical)
- Change in EuroQOL EQ-5D scores (continuous and categorical)
- Change in 6-minute walk distance (6MWD) (continuous and categorical)
- Reduction in acid GER by serial pH testing and GER questionnaire
- Quantitative change in HRCT fibrosis score and honeycombing

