10.1. Sample Size Determination and Randomization

We are planning to enroll approximately 58 subjects randomized in a 1:1 ratio to laparoscopic anti-reflux surgery or standard care. Patients will be allocated using a computer generated randomization scheme. Due to the unblinded nature of the study intervention, the randomization will not be stratified. If enough subjects randomized to surgery are unable to undergo surgery due to failure of insurance authorization or medical eligibility reasons, consideration will be given to rebalancing and/or adjusting randomization to insure sufficient subjects undergo surgery to meet the aims of the study.

In powering the study, we have considered the potential impact of PPI use for symptomatic GER (part of standard medical care) on the rate of FVC change in the no surgery group. Under the assumption that the use of PPIs will be partly effective, our statistical power will be reduced. Based on historical knowledge of change in FVC over time in patients with IPF a difference of 1.0 standard deviation over a one-year period would be approximately 0.25 liters. We believe that a treatment difference of that size would be both clinically meaningful and consistent with our preliminary data. We have conservatively estimated that 40% of individuals in the no surgery group will take PPIs on a regular basis for control of typical GER symptoms (i.e. heartburn and dyspepsia), and that PPIs are 50% as effective as surgery in reducing the rate of decline in FVC over time. With these adjustments, the expected effect size is reduced to 0.8 standard deviations. For that reason, this study is powered to detect an effect size of 0.8 standard deviations (or approximately 0.20 liters) in

the change in FVC between the two groups with a two-sided alpha of 0.05 and 80% power. The estimated number of subjects required for varying effect size and power are shown in Table 3. These calculations are based on the two-sample t-test with an increase in the sample size to allow for up to 10% withdrawal of consent.

Total subjects	Effect size	Two-sided alpha	Power
38	1.0	0.05	80%
52	1.0	0.05	90%
58	0.8	0.05	80%
76	0.8	0.05	90%
100	0.6	0.05	80%
134	0.6	0.05	90%

Table 3: Enrollment requirements for varying effect size and power

*Calculations allow for 10% withdrawal of consent.

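### Ordinary logistic regression for mortality and acute exacerbation may give no finite odds ratio at about 29 patients per arm; a Firth penalty is a cheap remedy

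*Combined protocol and SAP*

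**What the plan says.** Section 10.3 is the whole plan for the event endpoints: "Regression modeling approaches using either the logistic regression model or Cox proportional hazards regression model will be employed for binary and time-to-event endpoints". The sentence closes with the adverb *respectively*, so logistic regression goes with binary endpoints and Cox regression with time-to-event endpoints. The section adds that "Statistical significance will be defined at the two-sided 0.05 level". It names no test statistic (Wald, score or likelihood ratio) and no rule for an arm without events.

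Section 6.2 lists mortality and acute exacerbation as bare entries. It lists disease progression twice, once bare and once as "Time to disease progression", which implies that the bare entries are binary.

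On size, Section 10.1 states: "We are planning to enroll approximately 58 subjects randomized in a 1:1 ratio", with "an increase in the sample size to allow for up to 10% withdrawal of consent". On follow-up, Section 1 states: "Subjects will be followed for 52 weeks or until the time of lung transplantation or death".

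On purpose, Section 2.1 hypothesises that surgery "will reduce the incidence of acute exacerbation, hospitalization, disease progression and death", while Specific Aim 4 (Section 2.5) is worded more modestly: "We aim to explore the impact of laparoscopic anti-reflux surgery on key secondary endpoints".

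**The concern.** Maximum likelihood has no finite log odds ratio when one arm has no events. The fitted coefficient grows with each iteration and its standard error grows faster, so the Wald p-value drifts towards 1 however clear the split. With 29 patients per arm and an uncommon event, that is an ordinary result.

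At stake is what can be reported about death and acute exacerbation, two outcomes named in the study hypothesis. A trial with 6 events on standard care and none after surgery could be reported with no estimate and an uninformative p-value, although the data carry real evidence.

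**Working it through.** **Inputs.** From Section 10.1: 58 patients at 1:1, so 29 per arm; 10% withdrawal allowance. From Section 10.3: two-sided 0.05. Assumed, because the documents give no event rates: risks of 3 to 30% per arm.

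**The plan's own figure.** For an effect of 0.8 SD, two-sided 0.05 and 80% power, the exact two-sample t-test needs 26 per arm (power 80.7%). Then 52 / 0.9 = 57.8, rounded up to 58, as in Table 3. The documents give no power or event count for the event endpoints.

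**How often one arm is empty.** With risk p, an arm has no events with probability q = (1 − p)^29. With equal risks, exactly one arm is empty with probability 2q(1 − q).
- 3%: q = 0.4134; 2 × 0.4134 × 0.5866 = 0.485
- 5%: q = 0.2259; 2 × 0.2259 × 0.7741 = 0.350
- 10%: q = 0.0471; 2 × 0.0471 × 0.9529 = 0.090
- 15%: q = 0.0090; 2 × 0.0090 × 0.9910 = 0.018

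At 3, 5 and 10%, the share of these tables that is only 1 v 0 or 2 v 0 is 91, 77 and 41%. No test calls those significant (smallest p for 2 v 0: 0.092, likelihood ratio), so there only the estimate is lost.

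**p-values at 29 per arm**

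| Split | Likelihood ratio | Score | Firth | Wald | Fisher |
|---|---|---|---|---|---|
| 3 v 0 | 0.038 | 0.075 | 0.101 | unusable | 0.237 |
| 4 v 0 | 0.016 | 0.038 | 0.046 | unusable | 0.112 |
| 6 v 0 | 0.003 | 0.010 | 0.009 | unusable | 0.024 |
| 6 v 1 | 0.035 | 0.044 | 0.0497 | 0.075 | 0.102 |
| 8 v 2 | 0.032 | 0.037 | 0.041 | 0.052 | 0.079 |

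For 3 v 0 and 4 v 0 the printed Wald p runs from 0.69 to 1.0 depending on whether the fit stops after 8 or 25 iterations.

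**Firth estimate.** In this two-arm model, Firth's penalty amounts to adding 0.5 to each cell. For 6 v 0: (6.5/23.5) / (0.5/29.5) = 16.3, profile-likelihood interval 1.78 to 2169. For 4 v 0: (4.5/25.5) / (0.5/29.5) = 10.4, interval 1.03 to 1405.

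**Type I error.** All binomial tables at 29 v 29 were enumerated, and Wald was counted as not significant when an arm is empty.
- Likelihood ratio: 4.6% at 3% per arm, 6.7% at 4%, 8.1% at 5%, and a peak of about 8.9% near 7%.
- Score and Firth: 2.7% at 5% per arm, and at most 5.5% over 3 to 50%.
- Wald: under 0.1% at 5% per arm.

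**Power at 20% v 5%.** Likelihood ratio 46.7%, score and Firth 43.9%, Wald 15.8%. The gap between score and Wald is 0.4395 − 0.1575 = 0.282. Empty-arm tables with at least 4 events in the other arm supply 0.2259 × 0.8596 = 0.194 of it, about two thirds.

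**After 10% withdrawal (26 per arm).** At 5% per arm, likelihood-ratio type I error is 7.4% and Firth 2.2%. Power at 20% v 5% is 39.5% for Firth and 12.5% for Wald.

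**Higher risks.** Likelihood-ratio and Wald decisions differ in 4.0% of trials at 15% per arm, 2.6% at 20% and 1.1% at 30%.

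**The case against.** Several stronger readings are tempting, and the documents or figures do not support them.

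- *The plan leaves the type of these endpoints open.* A reader might infer this because neither is labelled. But *respectively* in Section 10.3 and the paired disease-progression entries in Section 6.2 point to binary, and Section 2.1 speaks of incidence. What remains is a missing label.
- *The test will be picked after the data are seen.* No test is named, but nothing in the documents says that the choice would be made that way.
- *The likelihood-ratio test is too liberal whenever events are rare.* At 3% per arm it is below nominal.
- *The weak Wald test is a second, separate defect.* Most of its loss comes from counting empty-arm tables as not significant. Without an empty arm the difference is narrower. At 26 per arm, 8 v 2 gives Wald p = 0.049, so that disagreement disappears.

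The rest of the case against has weight. Every rate is assumed, and the point nearly vanishes if the true risks are 15% or more. Aim 4 is exploratory. Score and likelihood-ratio p-values exist even with an empty arm, so the model is not useless there; only the estimate and the Wald result fail. Firth rejects in exactly the same tables as the score test at 29 per arm, so choosing it for the p-value alone would be preference. Fisher's test would not call 4 v 0 or 6 v 1 significant, whereas Firth does.

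What stands is that the stated model, followed as written, can fail to give an estimate for two outcomes in the study hypothesis, and a standard alternative does not.

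**Conclusion.** The point holds as a minor improvement to the method. If the risks of death or acute exacerbation are about 10% or less per arm, the planned logistic model has a 9 to 49% chance (equal risks of 10% down to 3%) of meeting exactly one empty arm and giving no finite odds ratio. In many of those trials the split is too small for any test, and the only loss is the estimate. The loss matters most when there is a real difference, such as 20% v 5%, where reliance on Wald results would cost about 28 points of power. Likelihood-ratio p-values would instead be liberal from about 4% per arm upward.

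This rests on assumed risks, an unadjusted two-arm model and 26 to 29 patients per arm. Above about 15% per arm the problem is small. The primary FVC analysis and the sample size of 58 are not affected.

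**What to change.** In Section 10.3, state that mortality and acute exacerbation are binary endpoints. Replace ordinary logistic regression for these two with Firth-penalised logistic regression on treatment arm, with a profile-likelihood 95% interval and p-value whatever the event counts, and report the counts per arm. State the time window: Aim 4 runs over 48 weeks, while Section 7.2 collects deaths to week 52.

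Patients who leave follow-up early, by withdrawal or transplantation, should not be coded as event-free by default. Report their number by arm, and add a sensitivity analysis that censors them, using Firth-penalised Cox regression or a log-rank test, named in advance. In simulations at 20% v 5% without early censoring, Firth Cox had 40.0% power against 43.9% for log-rank.

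The cost is a few sentences and a check by the data coordinating center that its software offers these options. Estimates shrink slightly: for 10 v 5 events the odds ratio is (10.5/19.5) / (5.5/24.5) = 2.40 instead of (10/19) / (5/24) = 2.53. Intervals with an empty arm are very wide. There is no power gain over the score test; the gain is a finite estimate, with an interval and p-value from the same prespecified model.

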will undergo preapproval for billing the laparoscopic anti-reflux surgery and related activities and tests to the subject's insurance (all other study procedures will be paid for by the study). In the unlikely event that a randomized subject is denied authorization, the subject will not have surgery but will be followed on an intention to treat basis. All subjects in the surgical arm will receive a bronchoscopy at the time of surgery. Bronchoscopy is a separate procedure from the surgical intervention. Bronchoscopy will be performed according to standardized protocol and samples (BAL and endobronchial brushings) will be collected. These patients will then undergo surgery according to study protocol (see section 8). They will have a post-operative visit with the surgeon at approximately 2 weeks to ensure appropriate recovery.

Subjects randomized to no surgery will be followed clinically. If there is evidence of significant disease progression (defined by a relative decline in FVC of \geq 10% over 24 weeks or longer), these patients will be allowed to undergo laparoscopic anti-reflux surgery as part of the clinical trial. These patients will otherwise complete the study visits as scheduled.

All subjects in the study will be provided with a home spirometer and instructed to perform spirometry daily throughout the course of the clinical trial. Subjects who are randomized to surgery will be instructed to halt daily spirometry from the date of their surgery until they return to the site for the week 12 visit.

Subjects will be blinded to the results of the home spirometry measurements. Subjects will be instructed to bring home spirometers to each study visit so that data can be downloaded and sent to the DCC for databasing. Subjects will have the option after study completion to keep the home spirometer for personal use.

Safety assessments: Subjects will be contacted by telephone for safety assessments in months where no study visit occurs (months 1, 2, 4, 5, 7, 8, 10, 11) and at week 52. The calls should visits will occur within 10 business days of their designation (e.g. month 1 will occur +/- 10 business days from the month 1 timepoint). One month is defined as 28 days. These phone calls will involve confirming the subject's vital status and asking questions about serious adverse events or adverse events related to the surgical procedure, for subjects randomized to surgery.

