10.2. Specification of the Primary Analysis

The primary endpoint will be change in FVC (in liters) from baseline to 48 weeks. A mixed model repeated measures (MMRM) analysis, will be used to compare differences in the FVC measurements across treatment groups at 48 weeks.²² Response variables are values of the FVC measured at baseline and every 12 weeks until study completion at 48 weeks. Covariates in the model will include treatment time terms and the baseline FVC values. Contrast estimates of differences between treatments (along with confidence intervals) will be used to estimate the treatment effect. The validity of this model in terms of meeting modeling assumptions will be assessed via standard modeling diagnostics and goodness-of-fit measures. The MMRM models will be implemented using PROC MIXED in SAS. For subjects randomized to no surgery who subsequently undergo surgery as part of the study (per protocol), post-surgical FVC measurements will be obtained but will not be included in the assessment of the primary endpoint. Instead, a 48 week FVC value will be imputed based on the pre-surgical FVC values obtained in each individual patient.

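### Safety calls do not prompt operated controls for surgical adverse events, and Section 10 does not say how harms after crossover surgery are analysed for Aim 3

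*Combined protocol and SAP*

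**What the plan says.** Section 2.4 (Aim 3) states: "We aim to determine the safety of laparoscopic anti-reflux surgery in patients with IPF and abnormal GER".

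Section 5.4 lets controls with a relative FVC decline of at least 10% over 24 weeks or longer cross over: "these patients will be allowed to undergo laparoscopic anti-reflux surgery as part of the clinical trial". The same section sets out telephone safety calls in months without a visit and at week 52. They cover vital status and "asking questions about serious adverse events or adverse events related to the surgical procedure, for subjects randomized to surgery".

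Section 7.2 requires all deaths and SAEs from randomisation to week 52, with a causality assessment. It also requires non-serious adverse events related to the surgery, with no limit by arm. Other non-serious events are not to be reported.

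Section 10.2 has a crossover rule for one outcome. For operated controls, "post-surgical FVC measurements will be obtained but will not be included in the assessment of the primary endpoint". The replacement for the data set aside is described in these terms: "a 48 week FVC value will be imputed based on the pre-surgical FVC values obtained in each individual patient". Section 10.3 gives MMRM for longitudinal secondary endpoints and says that logistic and Cox models "will be employed for binary and time-to-event endpoints, respectively", adding: "Statistical significance will be defined at the two-sided 0.05 level". Mortality, acute exacerbation and non-elective hospitalization are among those endpoints (6.2). No part of Section 10 names a safety set, a harm comparison, a risk window or a summary of AEs or SAEs. The one mention of intention to treat concerns surgery-arm subjects refused insurance authorization: "the subject will not have surgery but will be followed on an intention to treat basis".

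**The concern.** The same operation can be given in both arms, but the prompt for its adverse events follows the randomised arm. An operated control can have dysphagia, bloating or a wound problem and never be asked about it on a call. That information cannot be recovered at the analysis stage.

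The second part concerns counting. The authors foresaw that crossover would contaminate FVC and wrote a rule for it. No rule says where a death, SAE, exacerbation or hospitalization after the same operation belongs. Counting by randomised arm is the likely default and is valid for comparing treatment policies. It does not by itself give the safety of the operation, which is what Aim 3 asks. Harm from the operation would partly sit in the standard-care column, and any protective effect on these events would be diluted in the same way. The trial is open-label, so if the layout is not fixed now it could be chosen after the events are known.

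**Working it through.** **Step 1. Set the rules side by side for an operated control.**

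| Item | Source | Operated control covered? |
|---|---|---|
| Deaths and SAEs, with causality | 7.2 | Yes |
| Non-serious surgery-related AEs: duty to report | 7.2 | Yes |
| Non-serious surgery-related AEs: asked about on calls | 5.4 | No |
| Post-operative visit (no scheduled study procedures) | 8 | Yes |
| No office spirometry or DLCO within 8 weeks of surgery | Table 1 footnote | Yes, stated for either arm |
| Analysis rule, FVC in the primary endpoint | 10.2 | Yes |
| Analysis rule, death, exacerbation, hospitalization | 10.3 | Model given, no crossover rule |
| Analysis of AEs and SAEs | Section 10 | None, in either arm |

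Crossover needs at least 24 weeks of decline. The calls that remain after week 24 are months 7, 8, 10, 11 and week 52: at most five for one control, and at most three (months 10, 11, week 52) for a control who qualifies at week 36.

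**Step 2. Arm size.** The plan's figure reproduces. A two-sample t-test at 0.8 SD, two-sided alpha 0.05 and 80% power needs 26 per arm, or 52 in all; 52/0.9 = 57.8, rounded up to 58, which is 29 per arm.

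**Step 3. How many controls might qualify.** The documents give no crossover rate. Inputs: SD of one-year FVC change 0.25 L (10.1); assumed mean 48-week decline 0.10 to 0.20 L; assumed baseline FVC 2.5 to 3.5 L. With a linear individual slope, week 36 change is 0.75 of week 48 change, so qualifying by week 36 means a 48-week decline of at least 0.10 x baseline / 0.75.
- 3.5 L, mean 0.10 L: cut-off 0.467 L; z = (0.10 - 0.467)/0.25 = -1.47; 7.1%.
- 3.0 L, mean 0.15 L: cut-off 0.400 L; z = (0.15 - 0.400)/0.25 = -1.00; 15.9%.
- 2.5 L, mean 0.20 L: cut-off 0.333 L; z = (0.20 - 0.333)/0.25 = -0.53; 29.7%.

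If change accumulates as a random walk instead, and week 24 or week 36 may qualify, simulation puts the last case at 35.2%. The range is therefore about 7% to 35%, or 2 to 10 of 29. Not all who qualify would be operated on.

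**Step 4. Effect on a by-arm harm comparison.** Let b be the background SAE risk, q the surgical SAE risk and c the share of controls operated on. Assume that the whole surgery arm is operated on and that q is equal in both arms.
- Surgery arm: b + (1 - b)q
- Control arm: b + (1 - b)qc
- Difference: (1 - b)q(1 - c), against a true excess of (1 - b)q

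The share kept is 1 - c, whatever b and q are. With assumed b = 10%, in percentage points:

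| q (assumed) | True excess | c = 10% | c = 20% | c = 30% |
|---|---|---|---|---|
| 5% | 4.5 | 4.1 | 3.6 | 3.2 |
| 10% | 9.0 | 8.1 | 7.2 | 6.3 |
| 20% | 18.0 | 16.2 | 14.4 | 12.6 |

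The expected number of surgical SAEs in operated controls is 29 x c x q: from 29 x 0.10 x 0.05 = 0.15 to 29 x 0.30 x 0.20 = 1.74.

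**Step 5. Follow-up after late crossover.** Week 36 is day 252 and week 52 is day 364. A control who qualifies at week 36 has at most 364 - 252 = 112 days before new SAEs stop being reportable, less the wait for surgery.

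**The case against.** The strongest reply is that the serious harms are already secured. Every SAE is reported in both arms and needs a causality assessment; one submitted without it is treated as research-associated until clarified. Every operated subject has a post-operative visit, controls still attend weeks 36 and 48 with a physical examination, and the DSMB reviews surgical safety. All of this stands. It confines the collection gap to non-serious surgical events, which are still reportable but not prompted on calls.

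A reader might infer from the call wording that SAEs in operated controls are missed too. Section 7.2 does not support that.

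A reader might also infer that the plan sets benefit against unoperated controls and harm against a control arm that includes surgery. It does not say so. Only FVC in the primary endpoint has the unoperated-control rule; the other benefit endpoints have no crossover rule. No harm comparison is written at all, and the intention-to-treat sentence is about insurance refusal. A control arm containing surgical harm is what as-randomised tabulation would produce, not something that the plan states.

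Nor do the documents show that crossover would turn a clear harm signal into none. That would need a sizeable surgery-arm count with almost no background events in progressive IPF. Power for an SAE difference is low anyway: at 29 per arm and b = 10%, 16% for q = 10% and 41% for q = 20%, with no crossover.

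Finally, the shrinkage would be larger if crossovers carried a higher operative risk, but the documents give no figure for this. Section 4.2 reports 14 operated patients, with FVC from 40% to 99% predicted, and no complications.

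**Conclusion.** The point holds in two parts. First, the call wording in 5.4 is a stated rule which, if followed, under-collects non-serious operative harm in operated controls. This rests on the text alone. Second, Section 10 gives Aim 3 no analysis and limits its crossover rule to FVC in the primary endpoint. If harms are tabulated as randomised, the apparent surgical excess is smaller by about the share of controls operated on: 10% to 30% at an assumed 10% to 30%. That range is itself generous, since it is close to the share who would merely qualify. It assumes equal surgical risk in both arms and a fully operated surgery arm.

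In absolute terms this is fewer than two expected surgical SAEs in the control column under the assumptions used. The matter is therefore one of clear description, not of significance. The primary FVC analysis is not affected. The change is worth making because it is cheap and serves a stated aim of the trial.

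**What to change.** - **Section 5.4.** Tie the surgery-related call questions to having had the anti-reflux surgery, regardless of assignment. Table 1's footnote already works this way.
- **Section 10, new Aim 3 paragraph.** Report deaths, SAEs, acute exacerbations and non-elective hospitalizations by randomised arm with 95% CIs, showing operated controls' post-surgery events on a separate line within the control arm.
- **Same paragraph.** Add a descriptive table of events after surgery for all operated subjects, in columns by randomised arm, stating each column's follow-up and noting that it is shorter for late crossovers.
- **If controls are also censored at crossover**, label that a sensitivity analysis and say that the censoring is informative, because crossovers are selected for decline. It should not be the version weighed against the FVC result.

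The cost is one phrase in 5.4, one paragraph in Section 10 and two tables, with no new visit or test. The downside is that the operated-subjects table is not protected by randomisation and should be read as description only.
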